Specify your research question(s), study aims or hypotheses (do not indicate "see protocol")

Surgical site infections are a subset of healthcare-associated infections (HAIs) that affect 3-5% of all patients undergoing surgery and are associated with a 2-fold increase in patient morbidity and mortality, a 2-fold increase in hospital duration, and a 66% increase in the risk of intensive care unit (ICU) admission (1-4). The Centers for Disease Control (CDC) and the World Health Organization (WHO) consider HAIs as a devastating issue tied to antibiotic resistance and have highlighted three major goals for HAI prevention including the following: 1) Prevention of infections in patients undergoing surgery, 2) Prevention of patient-to-patient bacterial transmission, and 3) improvement in antibiotic stewardship (5-7). These recommendations apply to the perioperative arena where the contribution of intraoperative bacterial reservoirs to bacterial transmission events and postoperative infection development has been confirmed (8-10). Indeed, a multicenter study recently demonstrated that stopcock contamination occurred in 23% of surgical cases, was associated with increased mortality, and was linked by molecular typing to postoperative infection (9). Intraoperative bacterial reservoir isolates have also been directly linked to the causative organism of infection for 30% of 30-day postoperative HAIs. Finally, transmission of S. aureus has been confirmed in up to 39% of surgical cases and has been directly linked to postoperative infection development(11). As such, attenuation of perioperative S. aureus transmission is an important target for HAI reduction. Therefore, our primary objective is to reduce perioperative S. aureus transmission. Our

secondary objective is to examine the impact of reduced *S. aureus* transmission on the incidence of superficial and deep surgical site infections (SSIs).

I.6 ***Background and significance and/or Preliminary studies related to this project. (do not indicate "see protocol")***

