Surgical service lines will include orthopedic total joint, orthopedic spine, gynecology/oncology, thoracic, general, hernia, colorectal, open vascular, plastic, and open urological procedures. These lines will be randomized 1:1 to either the bundle of activities or usual care. The unit of randomization is the service line. The perioperative environment (the patient, the patient to follow, and all providers caring for the patient and the patient to follow) for the randomized service line (treatment or usual care) will be involved in surveillance. This means that all patients, all providers caring for those patients (changes day by day), and care environments (equipment and stopcock sets) will be involved in surveillance. Surveillance from treatment and control groups will yield *S. aureus* transmission events that will be processed to guide proactive improvements in the treatment bundle.

Treatment group (bundle) inclusion/exclusion criteria:

Inclusion criteria: Patients seen at UIHC who are scheduled to undergo surgery from providers in one of the service lines above, documentation of informed, written consent, >18 years of age, procedure requiring general/regional anesthesia.

Exclusion criteria: Lack of documented informed, written consent, patients <18 years of age, procedures outside of the surgical service lines listed above, not requiring general/regional anesthesia, patients not seen in the UIHC clinics, and an allergy to iodine/shellfish or chlorhexidine.

Usual care group (existing practice at UIHC) inclusion/exclusion criteria:

Inclusion criteria: Patients seen at UIHC who are scheduled to undergo surgery from providers in one of the service lines above, documentation of informed, written consent, >18 years of age, procedure requiring general/regional anesthesia.

Exclusion criteria: Lack of documented informed, written consent, patients <18 years of age, procedures outside of the surgical service lines listed above, not requiring general/regional anesthesia, patients not seen at UIHC, and an allergy to iodine/shellfish or chlorhexidine.

VI.14

Provide an estimate of the total number of subjects that would be eligible for inclusion in each of your study populations (include your control population if applicable)

We anticipate that >80% of all patients undergoing surgery in the surgical service lines above will be eligible for the study.

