This will involve use of a sterile ESwab to obtain nasal, axillary, and inguinal swabs. Nasal: the swab is to be inserted into each nares no more than 3/4 of an inch and rotated 360 degrees 10 times. Axillary: the swab will be applied to the middle of the armpit, pressed firmly against the skin, and rotated 10 times. Inguinal: the swab will be applied to the inguinal crease, pressed firmly against the skin, and rotated 10 times. After collection, each swab will be inserted into the collection medium (Aimes transport medium), the applicator stick snapped off as directed, and the cap placed on the tube to seal the contents.

Treatment Bundle:

Decolonization: Each patient in the treatment group will receive Povidone iodine treatment for their nose and potentially their surgical site on the day of surgery in the Day of Surgery Admissions(DOSA) area. The surgical team will approve and guide the application of the povidone iodine to the likely surgical incision site(s) or it will not be placed. The application of the povidone iodine to the inside of the nose will be guided by a member of the research team. 2% Chlorhexidine body Wipes are currently used in UIHC Day of Surgery Admission (DOSA) to help disinfect patient skin before surgery

and we will make sure that treatment patients are properly administered these wipes and educated on their use.

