Sample Processing: All samples will be sent to RDB Bioinformatics for processing. Results will be entered into the software. The software will guide testing to identify *S. aureus* transmission events. *S. aureus* transmission events will be processed to identify transmission stories, and transmission stories will be reported in the software platform to guide proactive improvements in the bundle.

Infection Tracking: The patient will be followed for 90 days postoperatively to identify and infection. Initial screening criteria will include an elevated white blood cell count, fever ($T > 38$ degrees), anti-infection order, culture, or office documentation of infection. If one or more criteria are present, the patient will undergo a full chart review to determine if they developed a healthcare-associated infection (HAI) as determined by National Healthcare Safety Network (NHSN) definitions. All patient cultures obtained for infectious workup by the usual healthcare teams will be saved by the clinical microbiology laboratory. Samples will be sent to RDB for analysis in order to determine if the organism was clonally-related to an organism isolated from one or more reservoirs during the perioperative period.

Confounding Factor Analysis: Information from the patient medical record will be collected by the study team: date and time of surgery, diagnosis, ASA status (a system for assessing the fitness of patients before surgery), age, comorbidities (the presence of one or more additional diseases or disorders co-occurring with (that is, concomitant or concurrent with) a primary disease or disorder), surgery type and duration, type of anesthesia provided, operating room number, gender, dirty or infected surgery (yes/no), preoperative location, postoperative location, and duration of anesthesia. Data will password protected and kept in microEMR.

All patients will be called at 90 days (Up to 3 attempts will be made) to determine if they developed an infection.

VII.E.7 *Will you attempt to recontact subjects who are lost to follow-up?*

No - those lost to followup will not be recontacted

VII.E.9 *Will subjects be provided any compensation for participating in this study?*

No

VIII. Risks

VIII.1 *What are the risks to subjects including*

- emotional or psychological

- financial

- legal or social

- physical?

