Reducing Perioperative S. aureus Transmission via use of an Evidence-Based, Multimodal Program Driven by an Innovative Software Platform (OR PathTrac)

9/20/2018

Statistical Analysis

Multiple statistical methods were used. For simplification, we list the statistical methods in the precise sequence they are reported in the results.

The Fisher exact test was used to compare patient and procedural demographic information for treatment vs control groups and for cases involving *S* aureus transmission. Similarly, the distribution of patients by ASA scores greater than 2 and by sex for enrolled vs eligible patients were compared by surgeon using the Mantel-Haenszel test.

The Fisher exact test was also used to examine the potential association of each of the covariates mentioned earlier with *S aureus* transmission. None were associated.

A 2-sided Wilcoxon-Mann-Whitney test was used to examine the association of treatment assignment with the number of transmitted *S aureus* isolates. Poisson regression was used to estimate the incidence risk ratio (IRR) of *S aureus* transmission for the independent variable of treatment. Poisson regression was used to estimate the IRR because the incidence of transmission was so large (ie, much greater than 10%) that the odds ratio estimated using logistic regression would be a biased estimator of the relative risk.²⁴ We repeated the analysis using multilevel Poisson regression clustering by surgeon or specialty.

The Fisher exact test was used to compare the proportion of patients in the treatment group with transmission events before vs after surveillance feedback and the proportion of patients with SSI with and without documented *S aureus* transmission. Poisson regression was used to compare the proportion of patients with SSI with and without documented *S aureus* transmission, clustered by surgeon.

The proportion of patients with SSIs was compared with the Fisher exact test. Time to infection was evaluated by Cox proportional hazard modeling. We repeated the analysis using multilevel Poisson regression clustering by surgeon and specialty.

There were no missing data for the primary and secondary outcomes. Calculations were performed using Stata version 16.1 (StataCorp). All P values were 2-sided, and P < .05 was taken to indicate statistical significance.

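### The between-arm SSI analyses name no adjustment for the recorded dirty/infected flag, although only a few whole service lines are randomised

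*Protocol*

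**What the plan says.** - **Outcome.** Protocol I.5 makes the effect of reduced transmission "on the incidence of superficial and deep surgical site infections (SSIs" the secondary objective.
- **Eligibility.** In Protocol VI.13 the treatment-arm exclusion list ends with "patients not seen in the UIHC clinics, and an allergy to iodine/shellfish or chlorhexidine". The usual-care list is almost the same. Neither excludes dirty or infected cases. VI.15 also allows patients to be consented on hospital floors and in intensive care.
- **Randomisation.** VI.13 states: "The unit of randomization is the service line". It lists ten lines. XI.2 speaks of up to 10 lines in the power analysis and of 6 in the analysis paragraph.
- **The flag.** Under Confounding Factor Analysis, VII.E.6 lists "dirty or infected surgery (yes/no" among the items taken from the medical record.
- **Infection ascertainment.** VII.E.6 says "Initial screening criteria will include an elevated white blood cell count, fever" and adds further triggers. A patient who meets one goes to full chart review against NHSN definitions.
- **SSI analysis.** The SAP says "The proportion of patients with SSIs was compared with the Fisher exact test" and "Time to infection was evaluated by Cox proportional hazard modeling". It then repeats the analysis with a multilevel Poisson model clustered by surgeon and specialty. No covariate, stratum or restriction is named for any of the three.
- **Adjustment elsewhere.** XI.2 allows modelling if there is imbalance, but for the transmission outcome and for three other variables (case, duration over 2 hours, discharge location). The SAP tests its covariates against transmission, not SSI. Its baseline comparison of the arms has no stated consequence for the SSI analysis.

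**The concern.** The protocol names a potential confounder and collects it, but no planned SSI comparison uses it. With individual randomisation of 1,000 patients this would matter little, because chance would roughly balance the flag. Here whole service lines are randomised, and they range from total joint and hernia to colorectal and open vascular surgery. If dirty or infected cases gather in some lines, one arm can receive a clearly larger share. Should those cases also have a higher SSI risk, the unadjusted comparison moves for a reason unrelated to the bundle, in either direction. Clustering by surgeon or specialty allows for correlation within clusters, but it does not adjust the treatment estimate for a patient-level factor that differs between arms.

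**Working it through.** **Plan's own figure.** There is none to reproduce. The documents give no SSI sample size, effect size or power; the figures in XI.2 concern transmission.

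**Inputs from the documents.** Background SSI rate 3-5% (I.5); 500 first patients per arm (XI.1); two-sided 0.05 (SAP).

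**Assumptions.** These are the shares of flagged cases, qT (treatment) and qC (control), the SSI risk r1 in flagged cases, and the SSI risk r0 in unflagged cases. I take r0 as 3%, 4% or 5%, borrowing the overall range. The documents give none of these four.

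**Step 1: shift with no bundle effect.** The crude risk in an arm is q × r1 + (1 − q) × r0. The difference between arms is therefore (qC − qT) × (r1 − r0). With r0 = 4%, in percentage points:

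| Imbalance in share | r1 = 8% | 12% | 16% | 20% |
|---|---|---|---|---|
| 10 points | 0.4 | 0.8 | 1.2 | 1.6 |
| 5 points | 0.2 | 0.4 | 0.6 | 0.8 |
| 2 points | 0.08 | 0.16 | 0.24 | 0.32 |

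For example, 0.10 × (0.20 − 0.04) = 0.016. Among 500 patients the top row is 2 to 8 SSIs, set against 0.04 × 500 = 20.

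**Step 2: crude risk ratio and false-positive rate, still with no bundle effect.** P is the simulated chance that the two-sided Fisher test gives p < 0.05 at 500 per arm (4,000 runs). The simulation treats patients as independent given their arm's crude risk.

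| r0 | qT vs qC | r1 = 10% | r1 = 20% | r1 = 30% |
|---|---|---|---|---|
| 3% | 2% vs 8% | RR 0.88, P 0.04 | RR 0.77, P 0.11 | RR 0.69, P 0.20 |
| 3% | 2% vs 15% | RR 0.78, P 0.09 | RR 0.60, P 0.33 | RR 0.50, P 0.64 |
| 5% | 2% vs 8% | RR 0.94, P 0.04 | RR 0.85, P 0.07 | RR 0.79, P 0.13 |
| 5% | 2% vs 15% | RR 0.89, P 0.06 | RR 0.73, P 0.20 | RR 0.63, P 0.48 |

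For example, with r0 = 3%, r1 = 20% and 2% vs 8%: (0.02 × 0.20 + 0.98 × 0.03) / (0.08 × 0.20 + 0.92 × 0.03) = 0.0334 / 0.0436 = 0.77. With equal shares (5% vs 5%) the RR is 1.00 and P is about 0.04. Stratifying by the flag gives RR 1.00 in every cell by construction.

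**Step 3: what stratifying does and does not repair.** Suppose the bundle has RR 0.70 in unflagged cases and 1.0 in flagged cases, with r0 = 5% and r1 = 20% under usual care.

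- *Equal shares, 5% in each arm.* Treatment: 0.05 × 0.20 + 0.95 × 0.035 = 0.04325. Control: 0.05 × 0.20 + 0.95 × 0.05 = 0.0575. The crude RR is 0.75. The Mantel-Haenszel stratified RR is also 0.75, because the strata are the same size in both arms.
- *Unequal shares, 8% treatment and 2% control.* The crude RR is (0.016 + 0.0322) / (0.004 + 0.049) = 0.0482 / 0.053 = 0.91. For the Mantel-Haenszel RR, the flagged stratum (40 vs 10 patients; 8 vs 2 SSIs) contributes 8 × 10/50 = 1.6 over 2 × 40/50 = 1.6. The unflagged stratum (460 vs 490 patients; 16.1 vs 24.5 SSIs) contributes 16.1 × 490/950 = 8.30 over 24.5 × 460/950 = 11.86. The ratio is 9.90 / 13.46 = 0.74.

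Stratifying removes the part due to imbalance (0.91 to 0.74). Only restriction to unflagged cases returns 0.70.

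**The case against.** **Chance, not systematic bias.** Under randomisation of lines an imbalance is chance variation between lines, and the multilevel Poisson model should carry some of it into the uncertainty. That is fair, and the concern should not be called systematic bias. The estimate from the allocation actually drawn still stays unadjusted.

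**The imbalance may be small.** With five equal lines per arm, a 10-point difference needs, for example, one line with 50% flagged cases and none in any other. A first patient must return a mailed swab kit, with a 10-day window before surgery as the goal, and XI.1 limits the work flow to patients seen in clinics. These features may keep flagged cases few. This stands, and it is why the table also shows 2 and 5 points. With 2% vs 8% and r1 = 10%, the Fisher rejection rate is no different from that with equal shares.

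**Counting infections already present.** A reader might infer that such infections enter as SSIs from day 0, since fever, white count or a culture could be positive for the condition being operated on. The documents do not support this. The triggers only lead to a chart review against NHSN definitions, and how that review treats infection present at surgery is not described.

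**Silence is not a decision.** The SAP does not name the flag. It does not say that the flag is left out, and it refers to covariates mentioned earlier in text that it does not contain. Its baseline comparison might reveal an imbalance, but nothing says that this would change the SSI analysis. The protocol also does not state when the flag is recorded; I treat it as baseline because it describes the operation.

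**Too few events.** At 3-5% of 1,000 first patients, about 30 to 50 SSIs are expected. The comparison is weak with or without the flag, but one binary term is feasible.

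**Conclusion.** The point holds in a limited form. Dirty or infected cases are eligible, the protocol lists the flag as a potential confounder, and no between-arm SSI analysis names an adjustment for it. Because 6 to 10 whole lines are randomised, an unequal share of flagged cases is plausible, and clustering does not adjust for it.

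No size can be asserted. The range of 0.4 to 1.6 points rests on three assumptions: 4% risk in unflagged cases, 8% to 20% in flagged cases, and a 10-point imbalance. If shares are equal, or flagged cases carry no extra risk, the shift is zero. A reader might set the range against a 30% reduction in SSI and conclude that the imbalance could equal the whole effect. That yardstick is the transmission target in XI.2; no SSI effect is stated. Nor should a reader conclude that stratifying would also undo dilution from infections that the bundle cannot prevent: Step 3 shows that it does not.

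This is a minor improvement to a secondary analysis and does not affect the primary outcome.

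**What to change.** In the SAP:

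1. Stratify the between-arm Cox model for time to infection by the dirty/infected flag.
2. Add the flag as a fixed covariate in the multilevel Poisson SSI model.
3. Report the number of patients and SSIs by arm and flag.
4. Keep the Fisher test, but label it as an unadjusted comparison.
5. Add an estimate restricted to unflagged cases as a sensitivity analysis, because items 1 and 2 address imbalance only, not dilution.

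The cost is SAP wording and one extra term in models with few expected SSI events. The variable is already collected, and eligibility, data collection and patient care do not change.

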IV.1 *Do you want the IRB to give this project*

Regular (expedited or full board) review

IV.2 *Enter the date you will be ready to begin screening subjects/collecting data for this project. (If you do not have a specified date, add "upon IRB approval")*
4/01/18

IV.3 *Are you requesting a [waiver of informed consent/authorization](#) (subjects will not be given any oral or written information about the study)?*
No

V. Other Committee Review

V.1 *Does this project involve any substance ingested, injected, or applied to the body?*

- *Do not answer yes, if the involvement includes a device, wire, or instrument*

• Yes

V.1.a *What is/are the substance(s):*

These are all currently used in care:

Nasal povidone iodine (Povidone-Iodine Solution 5%, 3MTM, St. Paul, MN 55144-1000)

2% Chlorhexidine Gluconate (CHG) Cloths, FDA-approved antiseptic solution (Sage Products LLC 2018 · [name])

We will also be using a catheter care product (Catheter Care Station, HubScrub™ and DOCit™, Mentor Ohio US 44060) that disinfects open or closed lumens with 62% isopropyl alcohol and includes a hand hygiene component with 62% alcohol.

V.1.b *Are any of these substances defined as a [Schedule I - V Controlled Substance](#)?*

No

V.2 *Are any contrast agents used for any purpose in this study?*

No

V.4 *Are all drugs or substances in this study being used within the FDA approved population (i.e., children, adults)?*

Yes

V.5 *Are all drugs or substances in this study being used within the FDA approved indication (i.e., disease, condition)?*

Yes

V.6 *Are all drugs or substances in this study being used within the FDA approved dose?*

Yes

V.7 *Are all drugs or substances in this study being used within the FDA approved route of administration?*

Yes

V.9 *Will any subject be asked to undergo a diagnostic radiation procedure (including radiographic, nuclear medicine, DEXA)?*

No

V.14 *Will any subject be asked to undergo a radiation therapy procedure (including external beam therapy, brachytherapy, or nuclear medicine therapy)?*

No

V.20 *Does this project involve the deliberate transfer of recombinant or synthetic nucleic acid molecules, or DNA or RNA derived from recombinant or synthetic nucleic acid molecules, into one or more human research participant?*

No

V.21 *Will any portion of this project be conducted in the CRU, or does it use any CRU resources?*

- No
- V.22 ***Will this project use:***

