Patients: Possible anxiety about properly following instructions on how to decolonize with povidone iodine. There is a rare but possible risk of topical hypersensitivity with topical iodine or chlorhexidine antiseptic solutions.

Providers: None apparent.

VIII.2

What have you done to minimize the risks?

- *If applicable to this study ALSO include:*
 - *How you (members of your research team at Iowa) will monitor the safety of individual subjects.*
 - *Include a description of the availability of medical or psychological resources that subjects might require as a consequence of participating in this research and how referral will occur if necessary (e.g. availability of emergency medical care, psychological counseling, etc.)*

Patients will be consented. Patients will receive thorough instructions for proper use of swab kits, Povidone iodine, and chlorhexidine. The consent process will require confirmation that there are no known allergies to shellfish, Povidone iodine, or chlorhexidine. The rare possibility of a hypersensitivity reaction to the topical Povidone or chlorhexidine antiseptic agents will be communicated. It will be recommended that they call their primary care doctor if they do develop a rash.

Providers will also have an opportunity to decline. Emails will be sent out to providers initially and the day before, and providers will have the opportunity to decline at any point the day of.

VIII.3

Does this study have a plan to have an individual or committee review combined data from all subjects on a periodic basis (such as summary or aggregate safety and/or efficacy data)?

No

IX. Benefits

IX.1

What are the direct benefits to the subject (do not include compensation or hypothesized results)?

None

IX.2

What are the potential benefits to society in terms of knowledge to be gained as a result of this project?

Successful implementation of this study will provide an organized, cost-effective pathway to reduce patient harm for up to 7% of patients undergoing surgery and could be extended hospital-wide to improve quality of care delivered to thousands of patients each year, save the hospital system billions of dollars, and address the issue of antibiotic resistance.

X. Privacy & Confidentiality

X.1

What are you doing to protect the privacy interests of the subjects?

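### No described study contact asks about topical hypersensitivity, so a report of no reactions would not support a rate or an upper bound (minor and cheap to fix)

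*Protocol*

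**What the plan says.** Protocol VIII.1 lists two risks to patients. One is anxiety about following the decolonization instructions. The other, and the only physical one, is this: "There is a rare but possible risk of topical hypersensitivity with topical iodine or chlorhexidine antiseptic solutions".

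The prompt in VIII.2 invites a description of how the local team will monitor individual safety, under the words "If applicable to this study ALSO include". The answer covers consent, instructions, confirmation that there is no known allergy, and a warning about reactions. For a reaction that does occur it says: "It will be recommended that they call their primary care doctor if they do develop a rash". It describes no report back to the study.

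Follow-up in VII.E.6 is directed at infection. The chart screen opens on a raised white cell count, fever, "anti-infection order, culture, or office documentation of infection". The telephone contact is described in the same terms: "All patients will be called at 90 days (Up to 3 attempts will be made) to determine if they developed an infection".

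**The concern.** The plan names a harm, and its one instruction for that harm directs the patient to someone other than the study team. If nobody on the team asks, the trial can count only the reactions that staff happen to see or that someone later finds in a chart. A statement that none was documented could then be read as meaning that none occurred. Reactions that were never asked about cannot be recovered at the analysis stage.

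The stakes are limited to what the trial can say about harm. That has some value, because IX.2 looks ahead to extending the program across the hospital. The transmission and surgical-site infection comparisons do not depend on it.

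**Working it through.** **Step 1: what each described contact is for.**

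- Screening question (VII.D.20): asks about known allergy before exposure. It lowers the risk but cannot detect a new reaction.
- Day-of-surgery iodine (VII.E.6, Decolonization): a team member guides the nasal application. No recording of a reaction is described.
- Operating-room sampling (VII.E.6, OR PathTrac surveillance procedures): swabs of nose, axilla and groin after induction and at case end, for culture.
- Recovery sampling (VII.E.6, Postoperative Surveillance Cultures; XI.1, Reservoir sampling): the same three sites and an area near the wound, for culture.
- 90-day chart screen and call (VII.E.6): infection.
- Record items listed under Confounding Factor Analysis (VII.E.6): no reaction item. That list is of confounders and need not be every field collected.

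None of these, as described, asks whether a reaction occurred.

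**Step 2: who is exposed, and where.** Only the first patient of a treatment pair receives the bundle (VII.E.6). Chlorhexidine wipes are already site practice, so that exposure is not confined to the bundle arm. The place of iodine use is unclear. The Decolonization text puts it in the admissions area on the day of surgery. The opening of VII.E.6 links the mailed kits to iodine decolonization in the treatment group, although its list of kit contents names no iodine. VII.D.28 allows 2 to 4 days of treatment before surgery.

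**Step 3: the denominator.** XI.1 states 500 treatment pairs. One pair per day × 5 days × 50 weeks × 2 years = 500, which reproduces the stated figure. The documents give no reaction rate, safety threshold or safety sample size.

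**Step 4: what complete ascertainment would support.** With zero events in n patients, the exact upper limit is 1 − a^(1/n).

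- n = 500, a = 0.05: 0.597%, or 0.60% (one-sided 95%).
- n = 500, a = 0.025: 0.735%, or 0.74% (two-sided 95%).
- For non-zero counts, the exact two-sided 95% intervals are 0.005% to 1.11% for 1 of 500 and 0.33% to 2.32% for 5 of 500.

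Counting bundle patients whose pair is later excluded changes little. At an assumed 2% to 10% exclusion, n is 500/0.98 = 510 to 500/0.90 = 556, and the one-sided limit is 0.59% to 0.54%.

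**Step 5: what zero recorded events would support under incomplete capture.** If a share s of reactions reaches the study, the recorded rate is p × s. The one-sided limit for the true rate p is then 0.597%/s, and the chance of recording none is (1 − p × s)^500. The values of s and p are assumptions, since the documents give neither.

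| s | Limit for p | Chance of none recorded, p = 1% | Same, p = 0.5% |
|---|---|---|---|
| 75% | 0.80% | 2.3% | 15.3% |
| 50% | 1.19% | 8.2% | 28.6% |
| 25% | 2.39% | 28.6% | 53.5% |

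Because s is unknown, no row can be chosen, and zero recorded reactions gives no defensible limit.

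**The case against.** The strongest case on the other side is that this matters little and may already be covered.

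- **Low risk.** V.1.a says of the products, "These are all currently used in care". V.5 asks, "Are all drugs or substances in this study being used within the FDA approved indication", and the answer is Yes. Known allergies are excluded. This stands, and it is why the point is minor.
- **Staff are present.** The team guides the nasal application and returns to several likely exposed sites during and after surgery. An immediate reaction could well be seen. This stands too, but seeing is not recording, and a delayed reaction after discharge falls outside these contacts.
- **Unseen material.** The consent pages, kit inserts and data forms are not available, and a request to report reactions would most naturally sit in the consent form. So the claim is limited to what the visible documents describe.
- **A chart count may be good enough.** At a true rate of 1%, capture of 50% to 75% would show at least one reaction with probability 91.8% to 97.7%. At 0.1%, even perfect capture shows none 60.6% of the time. This is correct, and it limits what is gained. It does not supply the missing capture share.

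A reader might go further and infer from the No in VIII.3 and the SAP's silence on safety that harms are not recorded at all. Neither supports that. VIII.3 concerns periodic review of combined data, not whether reactions are noted, and a descriptive count needs no statistical method in the SAP. Nor does advice to call a primary care doctor show that care would fall outside the hospital's own record.

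**Conclusion.** The point holds as a minor, cheap improvement. In the visible documents no contact asks about the only physical risk named, so a report of no reactions would not support a rate or an upper bound. With complete ascertainment, 0 of 500 would give 0.60% (one-sided 95%) or 0.74% (two-sided). With unknown capture, no limit can be stated.

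The 500 comes from the protocol; the reaction rates, capture shares and exclusion shares are assumptions. The conclusion also assumes that the unseen consent form and data forms do not already contain a reaction question. A reader might infer that patients are exposed to a material unmonitored danger, or that the efficacy results are compromised. The documents support neither: the products are described as in current use and within labelling, and the transmission and infection outcomes are collected separately. Severity is low.

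**What to change.** 1. For first patients in both arms, add one yes/no item on skin or nasal reaction at the existing recovery or pre-discharge sampling contact. Record with it which antiseptics were received, including any iodine used at home. Keep it on a study-held form, so that the data shared with the laboratory under X.6 do not change.
2. Add one back-up question to the 90-day call.
3. Unless the consent form already says so, ask patients to tell the study team about a reaction as well as their primary care doctor.
4. Report counts by arm for all treated patients, including those whose pair is later excluded, with an exact upper limit for the bundle arm and no test.

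The cost is a short form item, one call question and one descriptive table, with no extra visit. Capture will still be incomplete: recall at 90 days is late, some patients will not be reached, and delayed reactions after same-day discharge depend on self-report. The report should say so. The SAP is written in the past tense; if data collection has ended, the minimum is to give whatever count the charts yield and state that reactions were not systematically asked about.
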